3.1 Scholarly rationale and prior literature

Intestinal Microbiota in CF

Patients with CF have aberrant intestinal microbiota, as evidenced by decreased bacterial diversity and overabundance of pathogenic bacteria starting in infancy^{12,13}. Many factors in CF may lead to aberrant intestinal microbiota including frequent use of antibiotics, small bowel bacterial overgrowth, disturbed bowel motility, alterations in mucin clearance, pancreatic insufficiency, and intestinal inflammation^{14,15,16}. It is also possible that the habitual high-fat CF diet further promotes dysbiosis¹⁷. In a study of adolescents with CF, the severity of the CFTR mutation (presence of F508del) was associated with more abundant pathogenic bacteria such as *E. coli* and *E. biforme*, less abundant beneficial bacteria, and less microbial diversity¹⁸, suggesting an inherent dysbiosis caused by the CFTR defect. Rodent models of CF have mirrored the GI dysbiosis found in patients with CF in that rodents with mutations in the CFTR have less bacterial diversity and richness compared to wild type (WT) animals^{19,20}. *It is, therefore, clear that GI dysbiosis exists in patients with CF; however, the clinical significance of this state is unknown.*

Antibiotics alter intestinal microbiota

Patients with CF often receive combination antibiotic therapy to ensure coverage against the highly pathogenic bacteria *Pseudomonas aeruginosa*²¹. Broad spectrum antibiotic therapy alters the intestinal microbiota by disrupting local host-microbe communities, leading to decreased bacterial richness and diversity²². In a study of adults with CF during a period of stability, the number of IV antibiotic courses was inversely related to the intestinal microbiota diversity²³. A longitudinal study of a single patient with CF found that courses of antibiotic therapy decreased intestinal diversity and richness²⁴. *Therefore, wide spectrum antibiotic therapy remains a major factor in the intestinal dysbiosis found in patients with CF.*

Probiotics in cystic fibrosis

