Prebiotics are non-digestible dietary fibers that include inulin-type fructans and oligosaccharides that promote the formation of beneficial bacteria in the gut³³. Prebiotics do not contain bacteria and thus *are not* associated with bacteremia. A number of RCTs have confirmed that prebiotics can change gut microbiota in adults and children without CF^{34,35,36}. Additionally, some RCTs have demonstrated that changes in gut microbiota were associated with improved lung health. Ranucci et al reported in infants without CF enrolled in a 24 month RCT that an oligosaccharide-enriched formula protected against respiratory infections and increased the abundance of Bifidobacteria, a genera associated with protection against respiratory infections³⁷. Another RCT examining the prebiotics galacto-oligosaccharides and polydextrose found in children without CF found that the prebiotic formula was associated with fewer episodes of respiratory infections compared to children ingesting a standard formula³⁸. *Although prebiotics have demonstrated efficacy in promoting beneficial gut microbiota and improving respiratory infections in children without CF, no studies have been published using prebiotics in children and adults with CF. Prebiotics potentially have a better safety profile than probiotics since they are not associated with risk of bacteremia.*

Preliminary Results: Vitamin D status and intestinal microbiota in CF

Others have shown that vitamin D deficient mice or vitamin D receptor KO mice, have increased intestinal dysbiosis and GI inflammation³⁹. We explored the role for vitamin D in altering the intestinal microbiota in a pilot randomized placebo-controlled trial of adults with CF. We evaluated 41 adults with CF who were clinically stable and were not on recent IV antibiotics. Prior to any intervention, we found that vitamin D insufficient subjects displayed a higher abundance of potentially more pathogenic bacteria in the stool from the class of Gammaproteobacteria (class representing gram- bacteria such as *Pseudomonas*) (Figure 2).

[figure not shown]
Figure 2 Relative abundance of Gammaproteobacteria in the stool of adults with CF based on vitamin D status: vitamin D (25(OH)D) insufficient (<30 ng/mL) or vitamin D sufficient (≥30 ng/mL). Subjects with vitamin D insufficiency had more abundance of this class of potentially pathogenic bacteria compared to those with vitamin D sufficiency.

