Study synopsis: **60 adults will sign consent for screening with 40 randomized** with CF and vitamin D intake less than 2000 IU daily will be randomized in a 12-week RCT to: **1**) high-dose vitamin D₃ (50,000 IU weekly plus 12 g corn-derived maltodextrin/day as the prebiotic placebo); **2**) Chicory-derived inulin (12 g/day) prebiotic plus placebo vitamin D₃; **3**) combined vitamin D₃ and inulin; and **4**) placebo vitamin D₃ and placebo prebiotic. Stool and serum will be collected at baseline and at 12 weeks in the Clinical Research Center (CRC) of the NIH-funded Georgia Clinical and Translational Science Alliance (Georgia CTSA). We will assess the feasibility of this approach and collect preliminary data on changes in gut microbiota diversity (Shannon Index as primary), composition, and richness from baseline over time using 16S rRNA gene sequencing to inform future studies. Additional measures will include high-resolution stool and plasma metabolomics.

a. Enrollment:

- Patient Selection:** We will screen for study patients from adults with CF seen for routine care at the Emory CF Center. *Inclusion Criteria:* 1) male and female patients (age > 18 years) with confirmed CF by genetic mutation and/or sweat chloride testing, 2) ~~stable pulmonary function (no greater than 5% difference in FEV1% predicted from previous measurement within the past year)~~, 3) not currently on oral or systemic antibiotics for pulmonary exacerbation 4) use of CFTR modulator therapy is allowed *Exclusion Criteria:* 1) active GI disease, abdominal pain and/or diarrhea, 2) chronic kidney disease worse than stage 3 (eGFR < ml/min per 1.73 m²), 3) any vitamin D supplement use >2,000 IU or vitamin D analogue, **(patients who are taking more than 2,000 IU of vitamin D must agree to stop the vitamin D for 6 weeks and take less than 2,000 IU of vitamin D during the study)** 4) use of immunosuppressants or history of organ transplantation, or 5) current use of probiotics or prebiotics.
- Subject identification and initial screening:** We propose to consent **60 subjects** at least to randomize **40 subjects in the following arms**. We propose to study **40 subjects (10 in each arm)** in this 2x2 factorial design study (statistical considerations below).

Patients with CF who are scheduled for routine outpatient appointments will be pre-screened for eligibility by reviewing the electronic medical record.

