The following chart demonstrates when and from where data items will be collected. All of the sputum, and stool samples that are collected at enrollment and at the 3 month follow-up visit will be stored for future analysis of microbiota. Samples will be stored for long term storage for future studies only if subjects provide written informed consent with a second informed consent to grant long term storage of samples.

Data Items	Source and timeline of collection
Demographic Information	Self-report; Electronic Medical Record
Medical history (e.g., CF genotype , Dietary supplement and medication intake and antibiotic treatment and pulmonary exacerbations in the past 3 months)	Completed at enrollment. Self-report; Electronic Medical Record
Sputum microbiota analysis	Sputum Sample collected at baseline and month 3 during standard follow-up visit to the CF center for routine care.
Stool microbiota analysis	Stool Sample collected at baseline and month 3 during standard follow-up visit to the CF center for routine care.
Spirometry (including FEV1 and FVC) – as standard of care by inpatient and outpatient hospital team.	Obtained from electronic medical Record as pulmonary function tests are measured at baseline and 3 months as part of routine care.

8.1 Specimens to be collected: Specimens collected at baseline and follow-up visits will include stool and sputum.

8.2 Randomization: Subjects will be randomized to two interventions (vitamin D3 vs placebo) and (prebiotic vs placebo). Treatment assignments will be performed by blinded allocation according a schedule maintained by biostatisticians of the Georgia CTSA. The subjects' physicians will be informed of their participation in the trial, and the electronic medical record at Emory will be flagged indicating that the patient is participating in this trial to prevent the use of vitamin D or pre/probiotics. Our primary analysis will be intention-to-treat. If any subjects receive therapies that impact the microbiome such as antibiotics or immunosuppressant drugs, they will be analyzed in the groups to which they were randomized. In a secondary analysis we will make note of the subjects who these therapies and determine if there were any between group differences in the initiation of these therapies. The Investigational Drug Pharmacy will provide the randomization scheme.

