8.3 Archived specimens: Study subjects may sign an additional consent form for long term storage of samples. In addition to immune function, vitamin D has been linked to several non-skeletal disease states and conditions in the general population that may be applicable to CF. One example is diabetes, a common co-morbidity in patients with CF. It is, therefore, possible that remaining specimens will be banked for future study related to vitamin D in CF but beyond the specific scope of the current study. Any stored samples will be de-identified with a specific code whose identity can only be accessed by authorized study personnel appointed by the PI. Specimens will be stored in a -80° freezer at the Vitamin D and Bone Research Laboratory at the Emory University School of Medicine Division of Endocrinology and Metabolism.

9. Participant selection

9.1 Requested sample size and expected refusal or withdrawal rate: We propose to recruit 60 subjects to sign consent in order to have 40 randomized at the study site. This is a pilot study which will provide critically needed data to adequately power a larger study. The CF Foundation funded this as a pilot and feasibility study.

9.2 Inclusion/exclusion criteria:

We will screen for study patients from adults with CF seen for routine care at the Emory CF Center.

Inclusion Criteria: 1) male and female patients (age > 18 years) with confirmed CF by genetic mutation and/or sweat chloride testing, 2) stable pulmonary function (no greater than 5% difference in FEV1% predicted from previous measurement within the past year), 3) not currently on oral or systemic antibiotics for pulmonary exacerbation, and 4) use of CFTR modulator therapy is allowed

Exclusion Criteria: 1) active GI disease, abdominal pain and/or diarrhea, 2) chronic kidney disease worse than stage 3 (eGFR < ml/min per 1.73 m²), 3) any vitamin D supplement use >2,000 IU or vitamin D analogue, 4) use of immunosuppressants or history of organ transplantation, or 5) current use of probiotics or prebiotics.

9.3 Subject recruitment plan: Recruitment will be performed through referral from the outpatient CF Clinic.

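### Recent antibiotic courses are neither barred before baseline nor used in the analysis, so recovery after a course can contaminate the per-arm Shannon changes and SDs meant to size the larger trial

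*Combined protocol and SAP*

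**What the plan says.** - **Eligibility.** Sections 5.1 (Enrollment) and 9.2 both require that the patient be "not currently on oral or systemic antibiotics for pulmonary exacerbation". The condition covers present use only, and only for that indication. Neither list states an interval since the last course.
- **Effect of antibiotics on the endpoint.** Section 3.1 states: "Broad spectrum antibiotic therapy alters the intestinal microbiota by disrupting local host-microbe communities, leading to decreased bacterial richness and diversity". It concludes that "wide spectrum antibiotic therapy remains a major factor in the intestinal dysbiosis found in patients with CF".
- **The earlier pilot.** Section 3.1 describes the 41 adults evaluated there as "clinically stable and were not on recent IV antibiotics". It does not define how recent is recent.
- **A stop period exists for another exposure.** In section 5.1, patients taking vitamin D above the limit "must agree to stop the vitamin D for 6 weeks".
- **What is recorded.** The data chart in section 8 lists "antibiotic treatment and pulmonary exacerbations in the past 3 months" among the items completed at enrolment. No eligibility rule, stratification or analysis refers to it. The secondary analysis in section 8.2 concerns therapies started during the study.
- **Outcome and analysis.** Section 4.2 words the primary outcome measure as a comparison of richness pre- and post-treatment, while Aim 1 labels feasibility as the primary endpoint. Section 10 reports the diversity index at baseline and 12 weeks for each of the four treatment combinations. It also says that between-group differences will be determined, without naming a model or covariates.

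**The concern.** A participant sampled shortly after a course starts from a lowered diversity value and can be expected to rise over 12 weeks whatever the allocation. That rise enters each arm's change from baseline. If only some participants are affected, it also widens the spread of change. Section 10 gives the estimation of variability and effect sizes in each of the four arms as a main purpose of the pilot, so these are the quantities that would be carried forward. With 10 participants per arm, recently treated participants may also be unevenly spread by chance. The information needed to deal with this is collected but not put to use.

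**Working it through.** **Inputs from the documents (sections 5.1 and 10):** 40 randomised, 10 per arm; 20 v 20 for the vitamin D contrast; SD 1.2; planning differences 0.5 and 0.75; significance level 0.05. Section 10 does not say whether 1.2 is the SD of the index or of its change. I take it as the SD of change among participants without recent antibiotics.

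**Assumptions, not in the documents:** a share p = 10-40% recently treated, and a recovery R = 0.5-1.0 Shannon units over 12 weeks.

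**1. The plan's own power figures.** A two-sided t-test, 20 v 20, SD 1.2, gives 25.0% for 0.5 and 48.7% for 0.75. Section 10 states 29% and 56%. An SD of about 1.1 would give 28.9% and 55.6%. This mismatch is a separate matter and does not affect what follows; I use 1.2 as stated.

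**2. Within-arm change.** Spurious mean rise = p × R.

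| p | R = 0.5 | R = 1.0 |
|---|---|---|
| 10% | 0.05 | 0.10 |
| 25% | 0.125 | 0.25 |
| 40% | 0.20 | 0.40 |

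The largest value is 0.40/0.5 = 80% of the smaller planning difference. If someone ran a one-group test of change in 20 participants with no treatment effect, the rejection rate would be 5.4% at p = 10%, R = 0.5 and 25.9% at p = 40%, R = 1.0. The plan does not specify such a test.

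**3. Between-arm contrast, expectation.** Each arm gains p × R in expectation, so the difference is pR − pR = 0. Simulated type I error at 20 v 20 with p = 30% (40,000 trials) was 5.05% for R = 0.5 and 5.18% for R = 1.0, so it is not inflated.

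**4. Between-arm contrast, precision, at p = 25%.** SD of change = √(1.2² + R²p(1−p)); SE = SD × √(2/20).

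- No recently treated participants: SD 1.200, SE 0.379.
- R = 0.5: √(1.44 + 0.0469) = 1.219, SE 0.386, a rise of 1.6%.
- R = 1.0: √(1.44 + 0.1875) = 1.276, SE 0.403, a rise of 6.3%.

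At p = 30%, R = 1.0, power is 22.4% for 0.5 and 43.6% for 0.75, against 25.0% and 48.7% without recently treated participants.

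**5. Chance imbalance, at p = 25%.** For two independent Binomial(20, 0.25) counts, the probability of a difference of 4 or more is 0.199 (0.063 at p = 10%, 0.258 at p = 40%). This is two-sided, so about 10% in each direction. With R = 1.0, a difference of 4 moves the contrast by 4/20 × 1.0 = 0.20, about half of the SE of 0.379. For two arms of 10, a difference of 3 or more has probability 0.193 and moves the contrast by 3/10 × 1.0 = 0.30. This imbalance is the source of the extra variance in step 4, not an addition to it.

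**6. Effect on sizing the larger trial.** Sample size scales with SD². At p = 25% the ratio is 1.4869/1.44 = 1.03 for R = 0.5 and 1.6275/1.44 = 1.13 for R = 1.0.

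**The case against.** The strongest answer is the design. The trial is randomised and double-blind with a concurrent double-placebo arm, the primary analysis is by intention to treat, and the power statement is framed as a between-group difference. Recovery common to all arms appears under double placebo too and cancels in expectation. This stands. A reader might infer that recovery will be taken for a supplement effect; the documents do not support that, because between-group differences are planned and no single-arm test is. The wording of section 4.2 allows a within-arm reading but does not require it.

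Three further points carry weight:

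- The added noise is small even on generous assumptions (step 4), and section 10 says that significance is not the focus. But the pilot is meant to supply per-arm variability and effect sizes, so its purpose does not remove the point.
- If the larger trial recruits under the same criteria, antibiotic-related variability belongs in its SD. That is fair, and is why results split by history are more useful than exclusion alone: the sponsor can then size the trial either way.
- The baseline antibiotic history is recorded, so an imbalance could be found. True, but no stated analysis looks for it.

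A reader might also infer that a washout covering every antibiotic and indication, and also products barred only under "current use of probiotics or prebiotics", is needed. The documents do not go that far. The earlier pilot's description concerns IV antibiotics only, its interval is not given, and nothing indicates the size of any effect of past pre- or probiotic use. The vitamin D stop concerns one of the study interventions, so it is not a direct precedent. A washout would also cost accrual and representativeness. The FEV1 stability criterion might be offered as an indirect guard, but it is struck through in section 5.1 and kept in section 9.2; the two lists must be reconciled.

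**Conclusion.** The concern holds for the per-arm results. Nothing stops a participant from giving the baseline sample just after a course, and the plan makes no use of the history that would show it. On the assumed 10-40% and 0.5-1.0 units, the spurious within-arm rise is 0.05-0.40. At 25% the SD of change would be 1.22-1.28 instead of 1.2. The randomised contrast remains valid in expectation; its cost is about a 2-6% larger standard error and a realistic possibility of chance imbalance with 10 per arm. The gap in the text is certain. Its size is not, since it rests on an assumed prevalence and recovery and on reading 1.2 as the SD of change. This is worth correcting, but it does not undermine the trial.

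**What to change.** In section 10:

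1. Name the between-arm contrast of change in Shannon index, not the within-arm change from baseline, as the comparison of interest, and align the outcome wording in section 4.2 with it.
2. Adjust that contrast for antibiotic treatment in the 3 months before enrolment, as a single yes/no covariate.
3. Show per-arm change and SD split by the same history, descriptively, since the cells will be small.

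The cost is a few sentences and one degree of freedom; the data are already collected. The choice should be recorded before the allocation is unblinded. A yes/no indicator over 3 months does not separate a course that ended last week from one that ended ten weeks ago, so the adjustment will remove only part of the effect.

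Separately, the investigators should consider whether the eligibility lists in sections 5.1 and 9.2 should include an antibiotic-free interval before the baseline sample, in line with the earlier pilot. Its length and scope are theirs to set, weighed against the target of 40 randomised in 15 months.

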To address our hypotheses, we propose a pilot and feasibility, placebo-controlled, 2 x 2 factorial, double blind, randomized controlled trial (RCT) of vitamin D ± prebiotic in adults with CF and insufficient vitamin D status.

4.2) Specific aims:

Aim 1. Determine the impact of high-dose oral vitamin D and the prebiotic inulin on gut microbiota richness and diversity, and associated metabolomic changes, in stable outpatient adults with CF. In a 12-week RCT, we will assess the feasibility of a 2x2 factorial design RCT (primary-endpoint) to change major gut microbiome characteristics from baseline (Shannon diversity index) and targeted microbiome-dependent metabolites in 40 CF adults block-randomized to either: 1) high-dose vitamin D3 50,000 IU weekly (plus prebiotic placebo); 2) inulin (12 g/day) prebiotic (plus vitamin D placebo); 3) combined vitamin D3 and inulin; and 4) vitamin D placebo and prebiotic placebo.

At baseline and 12 weeks, we will determine changes in GI microbiota composition, diversity, and richness using 16S rRNA gene sequencing and microbiome-dependent metabolites pathways in stool and plasma using high-resolution metabolomics analysis.

[figure not shown]

Primary outcome measure: To compare phylotype richness of the respiratory and gastrointestinal tract microbiota before and after supplementation with high dose vitamin D ± inulin. These will be measured using ecological diversity measures including the Shannon index and the Species Richness index.

5. Study design and methods

5. 1 Overview of study design (Figure)

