3. **Informed consent and subject enrollment:** Informed consent will be obtained from the subject or the legally authorized representative. Amid the coronavirus crisis, informed consent will be obtained via secure videochat via Emory Zoom. The patient's identity will be confirmed with two forms of identification with full name and date of birth. The research coordinator or Drs. [name], [name], or [name] will obtain informed consent from the eligible subjects. The informed consent will be signed securely via DocuSign and returned via encrypted email. If the subject can not return via DocuSign, the subject will take a photo of the signed informed consent and return via encrypted email and mail in the wet signature. Once the DocuSign form is received or the photo/wet signature is received, the subject will be mailed the kits for stool and sputum collection as well as the vitamin D/prebiotic/inulin/placebo.
4. **Baseline studies:** Stool samples will be collected using a stool kit provided to the subject. Subjects will be provided in person or via return mail with a stool kit and a prepaid envelope to have the sample mailed directly to the study lab within the next 48 hours. These will be stored at -80 degree C. Subjects will provide a sputum sample in person or via return mail. Sputum samples will be collected via a sputum kit on day of visit and stored at -80 degree C. Relevant medical information will be extracted from the medical record and from questions to the participant.

5. Intervention:

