Vitamin D dose: We have conducted a number of studies demonstrating very effective use of vitamin D₃ at a dose of 50,000 IU weekly in the adult CF population. Our study in 2009 demonstrated that vitamin D₃ was superior to vitamin D₂ or UV lamp therapy in CF⁴³. Subjects receiving weekly doses of oral vitamin D₃ 50,000 IU for 12 weeks raised mean serum 25(OH)D concentrations from 21 ± 10 to 47 ± 20 ng/mL ($p < 0.001$) with 100% of subjects achieving a serum 25(OH)D greater than 30 ng/mL. We conducted a more recent study examining our dosing regimen of vitamin D3 50,000 IU vs placebo weekly for 12 weeks on gut microbiota in patients with CF and found that serum 25(OH)D increased significantly in the vitamin D₃ group from a mean of 24.99 ± 5.05 to 45.29 ± 21.01 ($p < 0.05$) compared to no change in placebo. Therefore, for this study we will use our established vitamin D dosing regimen of vitamin D₃ 50,000 IU once weekly for 12 weeks. As in past studies, we will obtain the vitamin D₃ and matching placebo capsules from Bio-Tech Pharmacal, Inc.

Inulin: Inulin is non-digestible fiber found in many food products. Inulin is also available as an over the counter supplement. Inulin will be provided from the brand name "Now Foods". This is a commercially available inulin supplement that is available in powder form. We have been in contact with the investigational pharmacy who will make sachets of 12 grams of Jetsu inulin for the active inulin group and 12 grams of

maltodextrin which is a food additive and commonly used as a control to inulin. Subjects will be asked to dissolve a sachet daily into a beverage of their choice (coffee, tea, water) and to ingest this daily.

All study drugs will be dispensed by the Investigational Drug Pharmacy.

- 6. Follow-up studies:** Patients will be followed throughout the duration of the study for 3 months. Subjects will provide their stool and sputum sample either in person or return by mail. For those subjects seen in person, participants will be seen for study follow-up visits at 3 months (+/- 4 weeks) as scheduled for their usual medical care (routine outpatient follow-up visits). Interim phone calls will be made to participants on a bi-weekly basis after week 1 to remind about taking pills. This will be done by the co-investigator. At the end of 3 months, we will obtain repeat stool and sputum samples from the entire cohort.

Procedures to be performed:

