9.4 Screening for eligibility: All patients with CF will be screened for eligibility at presentation to the CF clinic for routine visit by reviewing the subject's vitamin D intake. Screening will be completed daily by the research coordinator. Patients who have met the above inclusion criteria and have met none of the exclusion criteria on our initial assessment will be offered the opportunity to participate in our study. The study personnel will explain the study protocol in detail in the consent form as well as verbally. Any additional information regarding questions or concerns from potential or confirmed study participants will be provided by the study coordinator.

9.5 Withdrawal from study: Participants may withdraw from the study at any time. Automatic withdrawal occurs when a participant moves away from the center or refuses providing further blood, stool or sputum sample.

10. Statistical analysis

Statistical Considerations for Pilot Study:

We received this funding from the CF Foundation to test the feasibility of this 2x2 study design.

We will evaluate the feasibility of recruitment, retention, assessment and implementation of the proposed interventions. We wish to identify any potential flaws in the study design and potential challenges in the subsequent large-scale study. Our measures of feasibility will focus on metrics of recruitment, retention, acceptability & completion as adopted from the NIH/NCCIH . Our target metric of success is compared to our previous single intervention study with vitamin D (Table).

Feasibility Question	Feasibility Metric	Prior Rate	Target Metric of Success
Recruitment	Number of subjects screened a month	16.2/month	>15/month
Recruitment	Number of Enrolled/Screen Fails	1:4.05	1:4 Enrolled/Screened
Retention	Number of dropouts and reasons for dropout	13% (3 out of 23 enrolled)	<15%
Adherence	Number of subjects who adhere to assignment	Not recorded	>80%
Acceptability	Subject ratings for acceptability during and after participation	Not recorded	>3 on 5 point Likert scale
Completion	Number of subjects who complete all study procedures	73%	>70%
Completion	Duration from initiation to completion of pilot study	52 subjects in 15 months	40 randomized subjects in 15 months

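### Section 9.5 withdraws participants who move away although their month-3 samples could be mailed, and the feasibility table's yield row mixes two ratios with "enrolled" left undefined

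*Combined protocol and SAP*

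**What the plan says.** **Withdrawal.** Section 9.5: "Automatic withdrawal occurs when a participant moves away from the center or refuses providing further blood, stool or sputum sample". It makes no provision for collecting anything after withdrawal.

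**How month-3 samples arrive.** Section 5.1, item 6: "Subjects will provide their stool and sputum sample either in person or return by mail", and "At the end of 3 months, we will obtain repeat stool and sputum samples from the entire cohort". The mailing mechanism already exists at baseline; item 4 says "Subjects will be provided in person or via return mail with a stool kit and a prepaid envelope" and offers the same two routes for sputum. The chart in Section 8 says something different: both samples are taken at the routine clinic visit.

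**What the samples are for.** The primary outcome measure in Section 4.2 is "To compare phylotype richness of the respiratory and gastrointestinal tract microbiota before and after supplementation", so it has a gut part and an airway part. The same section also gives feasibility primary status: "we will assess the feasibility of a 2x2 factorial design RCT (primary-endpoint". Section 8.2 makes the primary analysis intention-to-treat.

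**Blood.** Section 8.1 names stool and sputum only. Section 4.2 plans "microbiome-dependent metabolites pathways in stool and plasma using high-resolution metabolomics analysis", the Section 5.1 synopsis says "Stool and serum will be collected at baseline and at 12 weeks", and Section 12 discusses venipuncture.

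**Feasibility table (Section 10).** The yield row's metric is enrolled over screen fails, its prior rate is 1:4.05 with no basis given, and its target is 1:4 enrolled over screened. The screening target is more than 15 a month (prior 16.2). The dropout target is under 15% (prior 3 of 23). The duration row sets 52 prior subjects in 15 months beside a target of 40 randomised in 15 months. Section 9.1 separates 60 consented from 40 randomised.

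**The concern.** Two feasibility measures are less well defined than they need to be, and one rule loses data without need.

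A participant who relocates can still post both specimens, yet 9.5 ends participation automatically. Month-3 samples that are not collected cannot be recovered. Section 10 relies on the 12-week diversity data in each of the four arms to size the next trial.

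The yield row is one of the trial's own success criteria. If its label, benchmark and target use different denominators, and enrolled can mean consented or randomised, whoever reports the result can choose after the event the reading that passes.

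**Working it through.** **1. The withdrawal rule, texts side by side**

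- Participant who moves: 9.5 withdraws them. Section 5.1 item 6 allows mailing and expects samples from all. The Section 8 chart expects a clinic visit. Under item 6 both specimens are obtainable; under the chart neither is. The three texts cannot all be followed.
- Participant who refuses, first reading (any one specimen type): someone who declines sputum is withdrawn and the stool they would still give is lost.
- Participant who refuses, second reading (all further sampling): nothing obtainable is lost.

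Size: with 10 per arm, each such loss is 1/10 = 10% of an arm's month-3 data for that specimen. If automatic withdrawals count as dropouts (not stated), each also uses up part of the allowance under 15%. The denominator is not stated either: 5/40 = 12.5% passes and 6/40 = 15.0% fails; 8/60 = 13.3% passes and 9/60 = 15.0% fails.

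**2. The table's own figures**

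The prior dropout rate reproduces: 3/23 = 13.0%. The prior yield of 1:4.05 cannot be rebuilt, because the documents give neither the number screened in the prior study nor how long screening lasted.

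**3. The yield label**

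For a ratio 1:r, the share of those screened who enrol is 1/(1+r) if r counts screen fails, and 1/r if r counts everyone screened.

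- Benchmark per screen fail: 1/(1+4.05) = 19.8%
- Benchmark per screened: 1/4.05 = 24.7%
- Target per screened: 1/4 = 25.0%

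**4. The meaning of enrolled**

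The protocol uses the word in more than one way. Section 5.1 item 3 pairs enrolment with consent. The 23 in the retention row equals the number randomised in the prior trial (Section 3.1, Preliminary Results). Section 12 speaks of people enrolled in an arm. At 1:4 per screened:

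| Enrolled means | Screened needed | Months at 15/month | Months at 16.2/month |
|---|---|---|---|
| 60 consented | 60 × 4 = 240 | 16.0 | 14.8 |
| 40 randomised | 40 × 4 = 160 | 10.7 | 9.9 |

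If the trial reaches its planned 60 and 40, the two definitions disagree for any total above 160 and up to 240 screened. The total is not given, so the range below is assumed. The first line takes the 15-month target less 3 months of follow-up.

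| Assumed screened | 60 consented | 40 randomised |
|---|---|---|
| 15 × 12 = 180 | 33.3% (meets) | 22.2% (misses) |
| 15 × 15 = 225 | 26.7% (meets) | 17.8% (misses) |
| 16.2 × 15 = 243 | 24.7% (misses) | 16.5% (misses) |

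**The case against.** The case for leaving the plan alone is reasonable in several respects.

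- Mailing is not settled: the Section 8 chart puts both samples at the clinic visit, and the synopsis places stool and serum collection in the research center. This stands, and it is why the texts need reconciling. It does not rescue 9.5, because item 6 is explicit about mail.
- The refusal trigger may simply mean refusing all sampling. This stands; only the moving-away trigger is free of ambiguity.
- Few people move within 12 weeks, and the consent form, which is not in the public document, may cover collection after withdrawal. Both are possible and neither can be checked.
- The yield label may be a slip: 1:4.05 is so close to 1:4 that both are probably per screened. That is plausible but unconfirmed, and it leaves enrolled undefined.
- No section makes the targets a binding go/no-go. This also stands.

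A reader might infer more than the documents support:

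- That 9.5 removes people from the analysis. It does not say so, and Section 8.2 keeps intention-to-treat.
- That 1:4.05 is wrong because 23 enrolled cannot produce it, or that the 52 proves the prior figures inconsistent. Any such reconstruction needs an assumed screening period. The benchmark is unverifiable, not shown wrong, and the 52 is merely undefined.
- That 16.0 months of screening shows the 15-month target to be unreachable. That figure holds only if screening rate and yield both sit exactly at their minimum; at the prior rate it is 14.8.
- That the blood trigger is a fault of 9.5. Several sections imply blood, and the wording of 8.1 may not be exhaustive.

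**Conclusion.** The point holds in two limited parts.

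First, 9.5 conflicts with the mail route and the whole-cohort promise in Section 5.1, and the Section 8 chart adds a third version. Following 9.5 forgoes both month-3 specimens of a mover and, on the one-type reading only, the other specimen of someone who declines one. The number is unknown and may be small; what matters is that the loss is avoidable.

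Second, the yield row has no single denominator. The label alone moves the benchmark between 19.8% and 24.7%, with no assumption beyond which basis applies. The definition of enrolled moves the screening requirement between 160 and 240, using only the planned 60 and 40. That the same data can both meet and miss the target rests on an assumed number screened; it is true at 180 and 225 but not at 243, where both definitions miss.

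No sample size changes. The blood mismatch and the undefined 52 are minor clarifications. The changes should be made because they are cheap and bear on measures to which the plan gives primary status.

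**What to change.** - In 9.5, end sample and data collection only when the participant withdraws consent for it. From anyone who moves or declines one specimen type, keep collecting, by mail if needed, the stool or sputum they still agree to give. This concerns samples and data only; it takes no position on study treatment.
- State which reading of the refusal trigger is meant, and reconcile 9.5, Section 5.1 item 6 and the Section 8 chart on how month-3 samples are obtained.
- Report month-3 retention separately for stool and sputum.
- Define enrolled once, as consented or randomised. Put the yield metric, benchmark and target all on enrolled per screened, and restate the benchmark from the prior study's records.
- Minor: reconcile the blood trigger with Section 8.1, Aim 1 (Sections 3 and 4.2), the Section 5.1 synopsis and Section 12, and say who the prior 52 subjects were.

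The cost is one or two sentences in 9.5, one definition, one relabelled row and one clarified row, from records the sponsor should hold. The downsides are a few mailed kits, two retention figures instead of one, and a benchmark that may look less favourable. Spirometry comes from routine-care records and may still be missing for movers. It should be recorded as missing, and it is no reason to forgo the mailed samples.
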